### 3.6 Table of endpoints/outcomes

Objectives	Outcome Measures	Timepoint(s) of evaluation of this outcome measure (if applicable)

Primary Objective To compare dynamic stability in cataract patients with Toric versus non-Toric IOLs
	
Dynamic stability: - movement of centre of mass and head tilting using wireless motion sensors.
	
Three timepoints:
 
 
1. pre-operation study visit and
 
2. post-operation study visit (3-6 months after first eye surgery).
 
3. post-operation study visit (3-6 months after second eye surgery).
 

Second Objectives To compare eye tracking characteristics, visual functions, risk of falls and quality of life in cataract patients with Toric versus non-Toric IOLs
	
Eye tracking characteristics: -area of interest by gaze pattern -Gaze duration on area of interest
 
Vision function include visual acuity, IOL rotation by degrees of rotation from intended position and degree rotation from the steepest meridian using special optometry equipment to look at the front of the eye (digital slit lamp and Pentacam)
 
Risk of fall will be measured by fear of falling and fall efficacy scale questionnaires. Vision related quality of life will be measured by CAT-PROM5 questionnaire.
	
Three timepoints:
 
 
1. pre-operation study visit and
 
2. post-operation study visit of first eye at 3-6 months after the surgery
 
3. post-operation study visit of second eye at 3-6 months after the surgery
 

## 4. TRIAL DESIGN

The study is a randomized controlled trial comparing the change of dynamic stability, gaze characteristics, visual function, and quality of life measurements between Toric and non-Toric intraocular lens (IOL) groups.

Vision and balance changes after bilateral implantation of Toric IOLs  
IRAS ID: 286913

The study is a double masked, parallel group design. 140 cataract patients with astigmatism  $>1.0D$  at the Royal Eye Infirmary (REI) of Derriford Hospital will be recruited and randomly assigned to either receive Toric IOLs or non-Toric IOLs for bilateral lens replacement surgery. The randomization will be conducted by the CI who is not involved in the surgical intervention nor the outcome measure assessments. The participants will not know which types of IOLs they are receiving and the study coordinator who assesses the outcome measures will be masked to the types of IOLs given to the participants. Study visits will be carried out before surgery, 3-6 months after first and second eye surgery.

## 5. TRIAL SETTING

This is a multi-centre trial. The screening and recruitment of participants will take place at the cataract clinic at the REI of Derriford Hospital, University Hospitals Plymouth NHS Trust. The intervention of Toric IOLs or non-Toric Monofocal IOLs cataract correction surgery will be carried out by the PI and his ophthalmologist team at the REI. The three study visits for outcome measurements will be carried out by masked assessors who are Allied Health Professionals (Optometrists or Physiotherapists) at the UoP (PAHC building).

## 6. PARTICIPANT ELIGIBILITY CRITERIA

140 cataract patients over the age of 50-year-old with astigmatism  $>1.0D$  undergoing bilateral intraocular lens replacement surgery will be recruited from the REI of the UHP over a three-year period. Three study visits will be arranged for each participant at the UoP (PAHC building) and will be followed up from before the cataract surgery to up to 12 months after the second eye cataract surgery.

### 6.1 Inclusion criteria

- Participants capable of giving informed consent
- Age 50 years or above
- Diagnosed with bilateral cataract with corneal astigmatism 1.00D or above
- Previously consented to routine NHS cataract surgery

### 6.2 Exclusion criteria

- Irregular astigmatism, Amblyopia

Vision and balance changes after bilateral implantation of Toric IOLs  
IRAS ID: 286913

- Any pre-surgical corneal complications or pathology such as Fuchs dystrophy, keratoconus
- Macular pathology, glaucoma, retinal disease, abnormal iris or pupil deformation
- Irregular or malformed eyelids such as ptosis, chalazion or severe blepharitis
- Previous corneal or intraocular surgery
- Any patient who does not have traditional phacoemulsification extraction will be excluded from the remainder of the study
- Incapable of giving informed consent due to lack of mental capacity, problems with communication or language and any conditions preventing the patient from fully understanding the procedures and nature of the study
- Predicted bilateral post-op corneal astigmatism of  $<1.50D$ , dilated pupil size smaller than 5mm
- Unable to walk independently with or without walking aids for 10 meters

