### 7.2 Consent

Prior to participant recruitment and any procedures for this study, ethical approval will have been obtained from both the Health Research Authority and the NHS Research Ethics Committee.

Potential participants will be asked to sign the written informed consent form on the same day as their pre-surgical routine visit at the REI (where they are consented for surgery) by a member of the research team. This is to accommodate the cataract surgery clinical pathway and to reduce the need for the patients to travel back to REI for signing the written informed consent form. Following the current cataract surgery clinical pathway, patients attend the REI for a pre-assessment cataract clinic appointment to discuss cataract surgery with their ophthalmology surgeons. If the patients would like to go ahead, consent for surgery is obtained during this appointment. The patients are then placed on a waiting list and the next time they are seen is on the day of surgery. With discussion with the sponsor, it is felt that obtaining consent at REI, where the patients will be having their surgery, is most appropriate in terms of safety and it also allows potential participants to discuss elements of cataract surgery directly with the clinic team or the surgeons. If the consent is obtained at the study site, the academic researchers, who are not ophthalmologists, would not be able to discuss the surgical aspect related to this study. There is a long period between this pre-assessment appointment and the surgery (several weeks or months). So, the patients will have considerable time to further consider about their participation. At each study visit, time will be provided for participants to ask questions or reconsider their participation.

All potential participants will be informed that participation in this research study will be entirely voluntary. No one will be coerced against their will and no undue influence will be exerted upon the patient. The participants have the right to refuse participation without giving reasons and their decision will be respected. The participants are also free to withdraw at any time from the trial without giving

Vision and balance changes after bilateral implantation of Toric IOLs  
IRAS ID: 286913

reasons and without prejudicing his/her further treatment. Data collected up to the point of withdrawal from the study will be used in the analysis.

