### **7.3 The randomisation schemes**

The PI will be responsible for recruitment of potential participants from the Cataract clinic at UHP and oversee the consent and eligibility process carried out by the study coordinator. All potential participants will be allocated a unique identification number. The CI, who is independent of the outcome assessments and interventions, will randomize the participants between the intervention and control groups. He will allocate a pseudonymous participant number from 1 to 140. Using simple randomisation with 1:1 allocation ratio through random.org, the 1 to 140 number will be randomly assigned into two groups (Toric IOLs versus non-Toric IOLs). The randomization list will then be passed to the PI, who when recruiting the participants at the pre-surgery clinic can know which type of IOLs (Toric or non-Toric) to prepare for the cataract surgery. At study commencement, each number will be allocated to one of the two groups randomly. This means that subjects are allocated to either arm of the study at the point of recruitment. The randomized list will be held by the PI, who delivers the intervention surgeries. The PI needs to know which lenses are allocated to the patients for surgery purposes but will not participate in the outcome assessment. The study coordinator who is the assessor of the outcome measures will be masked to the allocation of lenses.

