### **7.4 Blinding**

The participants will be masked to the interventions prior to the surgery. They will be told which IOLs they received at the end of their final visit. The CI will conduct the simple randomization for the participants through the random.org and he will be masked to the outcome assessment. The randomized list of participants will be passed to the PI and his ophthalmologist team to prepare the IOLs and deliver the

Vision and balance changes after bilateral implantation of Toric IOLs  
IRAS ID: 286913

cataract correction surgery. So, the PI cannot be masked to the intervention, but he is masked to the outcome assessment.

The outcome assessors for study visits will be masked to the interventions given to the participants. In the post-surgery study visit, the outcome assessors will carry out the dynamic stability reassessment before any visual assessment to ensure they are still masked to the primary outcome measures as the visual assessment will reveal which types of the IOLs the participants received.

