### 7.9 Withdrawal criteria

The participants can withdraw from the study at any time without giving any reason. Should there be a requirement to reassess eligibility, the PI or study coordinator may withdraw the participant if they do not meet the inclusion/exclusion criteria.

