### **10.6 Procedure(s) to account for missing or spurious data**

If the participants miss the study visit appointment without notification, they will be contacted for two more attempts within two months of the planned visit date. A letter of notification will be sent to their home address and if they have not replied within four weeks, they will be withdrawn from the study and any related data will be discarded.

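### Participants can be removed after allocation, by surgical technique (section 6.2) or eligibility recheck (section 7.9), and no analysis set keeps them in their randomised arm

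*Combined protocol and SAP*

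**What the plan says.** On timing, section 7.3 says: "This means that subjects are allocated to either arm of the study at the point of recruitment". The schedule in Appendix 2 marks randomisation at screening and baseline, and section 7.7 lists it after study visit 1. All three places put it before surgery.

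On removal, there are two rules.

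- Section 6.2 lists among the exclusion criteria: "Any patient who does not have traditional phacoemulsification extraction will be excluded from the remainder of the study". It does not say who applies this. Section 8.6 has the two eyes operated on separate occasions, about four months apart.
- Section 7.9 says that, if eligibility has to be reassessed, "the PI or study coordinator may withdraw the participant if they do not meet the inclusion/exclusion criteria".

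On who knows what, section 7.3 says of the PI: "The randomized list will be held by the PI, who delivers the intervention surgeries". Of the coordinator it says: "The study coordinator who is the assessor of the outcome measures will be masked to the allocation of lenses". Section 7.4 has balance tested first at each post-surgery visit, because "the visual assessment will reveal which types of the IOLs the participants received".

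On data from those who leave, section 7.2 says: "Data collected up to the point of withdrawal from the study will be used in the analysis". Section 10.6 says of people who miss visits and do not respond: "they will be withdrawn from the study and any related data will be discarded".

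On analysis, sections 10.3 and 10.3.2 plan a mixed ANOVA with lens type between subjects and time (before against after surgery) within subjects. Section 10.5, on the participant population, only restates eligibility. No section states that participants are analysed in the arm to which they were allocated.

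**The concern.** An exclusion criterion normally acts before randomisation and so cannot disturb the balance between arms. The section 6.2 rule refers to the rest of the study, which presupposes that the patient is already in it, and by then the arm has been assigned. Section 7.9 is open-ended in the same way: it is discretionary, it can be used at any time, and the people who may use it either know the lens or measure the outcomes.

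If the participants removed differ in prognosis from those who stay, and if removals differ between arms in number or kind, the comparison no longer has the protection of randomisation. Even with equal removals, the result describes a group defined partly by something that happened after allocation. At stake is whether the Toric against non-Toric difference in dynamic stability can be read as the effect of allocation in everyone randomised.

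**Working it through.** **1. Order of events.** Recruitment and allocation (7.3), then baseline visit 1, first-eye surgery, visit 2 at 3–6 months, second-eye surgery at about four months (8.6), and visit 3 at 3–6 months after that. The section 6.2 rule can act at either operation. Second-eye surgery may fall before or after visit 2.

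**2. What a removed participant contributes.** Section 7.2 keeps the data already collected. A participant removed at first-eye surgery has a baseline value and no post-surgery value, so a pre/post mixed ANOVA cannot use that participant. Section 10.3.2 sets the comparison as before surgery against after second-eye surgery, so a participant removed at the second operation also lacks the later value. No method for missing outcomes is given. In practice these participants leave the comparison.

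**3. The plan's own figure.** Sections 3.3 and 10.1 give f = 0.25, alpha 0.05, power 85%, 55 per group. For the between-group test in a repeated-measures ANOVA, λ = f²·N·m/(1 + (m − 1)ρ), with 1 and N − 2 degrees of freedom. With m = 2 time points and ρ = 0.5 (assumed; no correlation is stated), λ = 0.0625 × 110 × 2/1.5 = 9.17 and power is 85.1%, so 55 per group reproduces. With ρ at 0.3 or 0.7 the required total is 96 or 126. For dropout, 55/0.8 = 68.75, or 69, against the stated 70. The sample size is not in error.

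**4. Number removed.** No rate is given. Assuming 2–5%, 0.02 × 140 = 2.8 and 0.05 × 140 = 7, so about 3 to 7 people.

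**5. Power, if these losses come on top of the 20% dropout.** The plan expects 140 × 0.8 = 112 evaluable.

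| Extra removal (assumed) | Evaluable N | Power |
|---|---|---|
| 0% | 112 | 85.7% |
| 2% | 109.8 | 85.0% |
| 5% | 106.4 | 83.9% |
| 10% | 100.8 | 81.9% |

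**6. Bias, if all removals come from one arm.** For a fraction x removed whose mean is 1 SD below that of their arm, the remaining mean shifts by x/(1 − x) SD. If they are the worst outcomes in that arm, the shift is φ(z_x)/(1 − x) SD. For a single post-surgery value with 55 per arm, SE = √(2/55) = 0.191 SD. The two-sided type I error is then Φ(−1.96 + b/SE) + Φ(−1.96 − b/SE), where b is the shift.

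| x (assumed) | 1 SD worse: bias, type I error | Worst outcomes: bias, type I error |
|---|---|---|
| 2% | 0.02 SD, 5.1% | 0.05 SD, 5.8% |
| 5% | 0.05 SD, 5.9% | 0.11 SD, 8.8% |
| 10% | 0.11 SD, 9.0% | 0.20 SD, 17.6% |

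For two equal groups d = 2f = 2 × 0.25 = 0.5, so 0.05 SD is 0.05/0.5 = 10% of the planned effect. If the same fraction with the same deficit is lost from both arms, the shifts cancel and this bias is zero.

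**The case against.** The case for leaving the text alone has real substance.

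- Section 6.2 is mandatory and turns on the technique used, so it leaves little room for discretion.
- The cataract is extracted before the randomised lens goes in, and section 8.3 describes both lenses as plate-haptic, four-point-fixation designs placed in the capsular bag through a small incision. Nothing in the documents suggests that technique would differ by arm.
- Section 7.9 is conditional, and section 7.7 gives a harmless pre-surgery use: confirming suitability when an operation is delayed for a medical reason.
- The losses may fit within the 20% dropout allowance, and section 13.3 reports few dropouts in the team's earlier lens trials.

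All of this stands, and it limits the likely size. It does not change the order of events, supply the missing analysis set, or put a time limit on section 7.9.

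Two stronger readings are tempting. A reader might infer that only uncomplicated operations are analysed. That is not supported: section 9.5 lists posterior capsular rupture, zonular dehiscence and anterior vitrectomy as expected complications, and no section removes patients who have them. A reader might also infer that section 6.2 removals are decided by staff who have seen the outcomes. That section names no decider, and a first-eye removal precedes every post-operative study visit. The worry about outcome knowledge belongs to section 7.9, and for the coordinator's knowledge of the lens it begins only with the visual tests at visit 2.

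**Conclusion.** The point holds as a fault in the rules. Participants can be taken out after allocation, the two rules are not confined to facts known before it, and no as-randomised analysis is stated. That technique is settled at surgery is the ordinary reading; the documents do not say so outright.

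The effect on the result is possible but probably small. With 5% lost from one arm only and 1 SD worse, the bias is about 0.05 SD and type I error about 5.9%; power falls from 85.7% to 83.9% if 5% are lost overall on top of dropout. The larger figures in the table need higher rates or removal of exactly the worst outcomes in one arm. Every rate, the one-arm loss and the 1 SD deficit are assumptions, and the documents give no reason to expect removals to differ by arm. The case for change rests on the rule being avoidable at little cost, not on a demonstrated bias.

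**What to change.** 1. Take the phacoemulsification line out of the exclusion criteria as a reason to end participation. State that, once randomised, participants stay in research follow-up whatever extraction technique was used. This concerns study visits and analysis only, not the choice of operation.
2. In section 10, define the primary analysis set as all randomised participants in their allocated arm, and say how missing post-surgery values are handled.
3. In section 7.9, limit withdrawal on eligibility grounds to errors in information recorded before randomisation, judged by someone without knowledge of arm or outcomes.
4. Keep a per-protocol set (phacoemulsification in both eyes, allocated lens received) as a sensitivity analysis only.
5. Reconcile sections 6.2, 7.2, 7.9 and 10.6, so that one rule governs what happens to the data of anyone who leaves: at present section 7.2 keeps them and section 10.6 discards them after missed visits.

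The planned total of 140 does not change. The cost is protocol and SAP wording, a few more follow-up visits for people already enrolled, and perhaps slight dilution of the estimate.

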## 2. RATIONALE

Cataract is one of the major causes of visual impairment and blindness in the aging population. In UK, cataract alone accounts for over a third of the cases of vision impairment in those over 75 years. The Royal College of Ophthalmologists estimated a growth in prevalent cataracts by 43-57% between 2015 and 2035, causing around 50% increase in the expected number of cataract operations over the next 20 years. During cataract correction surgery, artificial lenses, otherwise known as intraocular lenses (IOLs), are used to replace the natural crystalline lens within the eye. By selecting IOLs of appropriate lens power, the pre-existing refractive error of the eye such as short-sightedness can be corrected during the IOLs implantation (Asbell *et al.*, 2005). Routine pre-operation assessment by ophthalmologists usually takes place 2-4 week before the cataract surgery. The ophthalmologist will select the appropriate IOLs by measuring of the axial length of the eye and the curvature of the cornea- the front clear covering of the eye. Implantation of the standard monofocal IOLs can only correct spherical refractive errors (near or far eyesight). Any preoperative astigmatism- imperfection of cornea curvature, can still affect the visual acuity and spectacle dependence after the operation.

Astigmatism is measured in the unit called dioptres (D). People with 1.5D or more usually need to wear contact lenses or spectacles for clear vision. Around 19-22% of the total population has over 1.50DC of corneal astigmatism at the time of cataract surgery (Swampillai *et al.*, 2020). A UK study of 1230 eyes in an NHS cataract clinic even reported about 40% of the patients attending routine cataract surgery had more than 1.00D astigmatism (Khan and Muhtaseb, 2011). It is estimated that patients are 34 times more likely to use spectacles per dioptre of astigmatic error in the better eye (Wilkins *et al.*, 2009). Uncorrected astigmatism not only increases spectacle dependence, even of relatively small amount, it can also result in reduction of visual performance (Read *et al.*, 2014). Reduced vision has been shown to link with poor balance or mobility (Lord, 2006) (Lord *et al.*, 2010) (Black and Wood, 2005). Oblique astigmatism (where the principal meridians are not orientated vertically or horizontally) also proved to affect balance and alter foot placement on steps (Johnson *et al.*, 2013). This could then

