### **10.2 Planned recruitment rate**

140 participants will be recruited over three-year period (minimal sample size of 110 plus 20% drop out rate estimation)

According to latest data from the National Ophthalmology audit database by the Royal College of Ophthalmologists, the REI of UHP performed 2525 cataract between 1st of September 2018 to 31st August 2019. The PI who performed cataract surgery at the REI reported around 3000 cataracts surgery were performed last year and the number is estimated to be similar this year. Due to COVID, there were longer waiting list and the waiting time between first and second cataract surgery at UHP has increased to about 4 months.

Approximately 40% patients undergo cataract surgery on both eyes (Jaycock, 2009 #281) (Day, 2015 #282). Among patients eligible for cataract surgery in NHS, 42% were reported to have mild to moderate astigmatism ( $>1.0$  D) (Day, 2019 #283). Therefore, it is estimated about 500 patients at REI annually will meet the inclusion criteria (needing cataract surgery in both eye with mild-moderate astigmatism) and our target for 140 participants out of the potential 1500 patients over three year

Vision and balance changes after bilateral implantation of Toric IOLs  
IRAS ID: 286913

should be a feasible number (10% of potential eligible patients), especially with the increasing number of cataract surgeries done every year.

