#### 10.4 Subgroup analyses

Within the Toric IOLs group, a subgroup of participants presented with post-surgery IOL rotation > 5 degree will be isolated to compare the outcomes. This subgroup of participants is very likely to need

Vision and balance changes after bilateral implantation of Toric IOLs  
IRAS ID: 286913

another adjustment surgery. Their data will inform the impact of IOLs rotation on surgery complications and whether such rotation may be related to degree of astigmatism.

In both the Toric IOLs and non-Toric IOLs group, subgroups of different degree of astigmatism: mild (<1.50), moderate (1.5-3.0) and severe (3.0+) will be differentiated to compare the outcomes to help inform if Toric IOLs offer similar beneficial effect across cataract patients with wide range of astigmatism. This will help to identify which patients should be referred for Toric IOLs and support evidence-based practice.

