### **10.5 Participant population**

Participants will be adult cataract patients of any sex, aged 50 years or above with astigmatism >1.0D who have already consented for bilateral cataract correction surgery at the REI of Derriford Hospital.

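### The 1.50 D exclusion in section 6.2 does not fit the >1.0 D population label, the mild subgroup in section 10.4 or the eligible pool in section 10.2

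*Combined protocol and SAP*

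**What the plan says.** The inclusion list in section 6.1 reads "Diagnosed with bilateral cataract with corneal astigmatism 1.00D or above". The trial summary and sections 3.1, 4, 6 and 10.5 describe the population as >1.0 D. Section 6 speaks of "140 cataract patients over the age of 50-year-old with astigmatism" >1.0 D, and section 10.5 of adults "aged 50 years or above with astigmatism >1.0D who have already consented for bilateral cataract correction surgery".

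Section 6.2 excludes "Predicted bilateral post-op corneal astigmatism of" <1.50 D. The same bullet also carries an unrelated pupil-size criterion. The protocol does not say whether *bilateral* excludes a patient when either eye is below 1.50 D or only when both are.

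Section 10.4 plans, in both arms, "subgroups of different degree of astigmatism: mild (<1.50), moderate (1.5-3.0) and severe (3.0" and above). The stated purpose is to see whether the benefit is similar over a wide range of astigmatism and to identify who should be referred for Toric lenses. It does not say whether the bands use pre-operative or post-operative values, corneal or refractive astigmatism, or which eye classifies a participant.

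Section 10.2 estimates about 500 eligible patients a year from the >1.0 D prevalence, or 1500 over three years, so that 140 is about 10%.

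**The concern.** The 1.50 D exclusion removes the part of the population that the mild band is meant to describe. Three things are at stake.

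- **Referral aim.** Section 10.4 is meant to guide who should be offered a Toric lens. It cannot do this for patients with 1.00-1.49 D in both eyes if none are enrolled. An estimate from a small or mixed group labelled mild could be mistaken for evidence about them.
- **Population label.** A report describing participants as >1.0 D would overstate the range studied.
- **Feasibility.** The recruitment case in section 10.2 is built on a pool to which the exclusion has not been applied.

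The undefined word *bilateral* adds a practical risk. Two screeners could apply different eye rules, and section 7.9 allows participants to be withdrawn if eligibility is reassessed and not met.

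**Working it through.** **Inputs, all from the protocol**

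- Annual volume (section 10.2): "around 3000 cataracts surgery were performed last year", as reported by the principal investigator; the audit figure is "the REI of UHP performed 2525 cataract".
- Share having both eyes operated (section 10.2): 40%.
- Share above 1.0 D: 42% (section 10.2) or about 40% (section 2).
- Share above 1.50 D (section 2): "Around 19-22% of the total population has over 1.50DC of corneal astigmatism at the time of cataract surgery".

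**1. The plan's own pool.** Volume × bilateral share × share above 1.0 D = 3000 × 0.40 × 0.42 = 504 a year, against about 500 stated. Over three years this is 1512, and 140/1500 = 9.3%, stated as 10%. The figure reproduces, but only if the 1.50 D exclusion is left out.

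**2. Share of the >1.0 D population removed, if a patient's two eyes agree.** Removed = 1 − (share above 1.50 D)/(share above 1.0 D).

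- 1 − 0.22/0.40 = 45%
- 1 − 0.22/0.42 = 48%
- 1 − 0.19/0.40 = 53%
- 1 − 0.19/0.42 = 55%

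The range is 45-55%. If recruitment followed the stated label, 140 × 0.45 = 63 to 140 × 0.548 = 77 participants would fall in the 1.00-1.49 D band.

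**3. The same share if the two eyes are independent.** This is an assumption, with both eyes above 1.0 D. Let q be the chance that an eye is above 1.50 D: q = 0.19/0.42 = 0.452 to 0.22/0.40 = 0.55.

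- Excluded only when both eyes are below 1.50 D: (1 − q)² = 0.55² = 30% to 0.45² = 20% removed.
- Excluded when either eye is below 1.50 D: 1 − q² = 1 − 0.205 = 80% to 1 − 0.3025 = 70% removed.

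**4. What is left in the mild band**

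- Either-eye reading: both eyes must reach 1.50 D on the predicted value. Only patients below 1.50 D on the subgroup's measure but not on the exclusion measure could be mild, so the band is nearly empty.
- Both-eyes reading: nobody is mild in both eyes on the exclusion measure, and only patients with one mild eye remain. Mild eyes are 0% of enrolled eyes if the eyes agree perfectly. If they are independent the share is q(1 − q)/[1 − (1 − q)²], which is 0.248/0.700 = 35% at q = 0.452 and 0.2475/0.7975 = 31% at q = 0.55.

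**5. The pool with the exclusion applied, eyes agreeing**

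| Volume | Per year at 19-22% | Three years | 140 as a share |
|---|---|---|---|
| 3000 | 3000 × 0.40 × 0.19 to 0.22 = 228-264 | 684-792 | 20-18% |
| 2525 | 2525 × 0.40 × 0.19 to 0.22 = 192-222 | 576-667 | 24-21% |

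**6. Sample size.** The 55 per group in section 10.1 rests on effect size 0.25, 85% power and a 0.05 level. No astigmatism threshold or prevalence enters it.

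**The case against.** The strongest reply is that an inclusion floor followed by a stricter exclusion is ordinary screening. Sections 6.1 and 6.2 also name different quantities: corneal astigmatism at diagnosis and a predicted post-operative value. Section 7.1.2 has ophthalmologists check both lists, and section 13.5 bars anyone who fails either. This stands: the two lists can be applied together, and the exclusion governs. It does not rescue the >1.0 D label, the mild band or the section 10.2 count, none of which reflects the combined filter.

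Second, how empty the mild band is depends on terms that section 10.4 leaves open. This also stands. Under the both-eyes reading, patients with one mild eye could be numerous, and bands based on refractive astigmatism could hold some mild cases. A reader might infer that the mild subgroup must be empty, or only a few stray cases. The documents support that only under the either-eye reading. What holds under both readings is that nobody is below 1.50 D in both eyes on the exclusion measure.

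Third, 45-55% is not a firm figure. The prevalences come from different cited sources, are quoted for patients at cataract surgery rather than for predicted post-operative values, and say nothing about how a patient's two eyes relate. This stands too, and the wider range in step 3 belongs beside it.

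**Conclusion.** The point holds, and it concerns text that is wrong as written rather than detail left out. The population that passes both eligibility lists is narrower than the label says, cannot answer the mild-band referral question for patients with 1.00-1.49 D in both eyes, and is smaller than the pool used for feasibility.

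Assuming that the quoted prevalences apply to predicted post-operative values in patients having both eyes operated, about 45-55% of the >1.0 D population is removed if the two eyes agree. With independent eyes it is about 20-30% under the both-eyes reading and 70-80% under the either-eye reading. With agreeing eyes the pool is about half of that stated. Independent eyes would make it larger under the both-eyes reading and smaller under the either-eye reading.

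Two stronger readings should be resisted. A reader might infer that the >1.0 D population would largely cease to exist. It would not: every patient at or above 1.50 D is also above 1.0 D, and only the 1.00-1.49 D part is lost. A reader might also infer that the main comparison is undermined. Section 3.1 compares the lenses in cataract patients with astigmatism and makes no separate claim for 1.00-1.49 D, so the primary objective is unaffected.

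**What to change.** The sponsor should reconcile sections 6.1, 6.2, 10.2 and 10.4. They should state one measure (pre-operative or predicted post-operative corneal astigmatism) and say whether *bilateral* means either eye or both. Only the astigmatism clause of the section 6.2 bullet should be edited; the pupil-size criterion beside it must stay as it is.

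While the current exclusion stands:

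- give the range actually enrolled in the summary and sections 3.1, 4, 6 and 10.5;
- drop the mild band from section 10.4, define the measure and eye used for the remaining bands, and limit the referral conclusion to the range enrolled;
- restate the pool and recruitment share in section 10.2 with the exclusion applied and its assumptions given.

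These are wording changes and need no new data. The cost is a narrower population claim and a less favourable feasibility figure. Which threshold is right is for the sponsor to decide.
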